4.1. Setting and participants

This study will include GMC registered doctors across the broad spectrum of medical specialties, from general practice in community clinics to specialist hospital-based outpatient and inpatient services.

Inclusion criteria

- GMC registered doctors from any areas of specialty and NHS healthcare services, including trainees on rotation in NHS services.
- Working either part-time or full-time in a clinical role.

Exclusion criteria

- Currently accessing or referred to any concurrent psychological intervention delivered by a mental health professional (this specifically refers to talking therapies for mental health problems).
- Doctors that are currently not in active clinical service at the time of recruitment (e.g., on sick leave, maternity leave or suspended for any reason).
- Doctors that work in a purely managerial, supervisory or educational role (e.g., not in clinical practice at the time of recruitment).

4.2. Intervention

This will be a group-based, digitally-enabled (video call) intervention based on the Mind Management Skills for Life Programme. This intervention was developed by [name] based on a model of the human mind elaborated in the book called The Chimp Paradox (Peters, 2012). The model is based on developments in neuroscience and psychological theory. It offers practical strategies and skills for the individual to learn how to: (1) gain insight into how their mind is working; (2) understand and recognise their thoughts, behaviours and emotions; (3) better manage themselves to become the person they would like to be. This intervention has been implemented in the world of elite sport, with public sector organisations, in the entertainment sector, in the corporate sector and with individuals over the past two decades. A number of (unpublished) small pilot studies have been conducted using this intervention with groups of NHS staff, both in primary and secondary care. These pilot programmes have shown preliminary indications that the Mind Management Skills for Life Programme could lead to improvements in the quality of life and wellbeing of the NHS staff in both their personal and professional lives. A recent randomised controlled trial investigated the effect of the Mind Management Skills for Life Programme on burnout and mental wellbeing in a large sample of mental health nurses (N=173), providing evidence that this intervention led to improvements in burnout and wellbeing (Laker et al., 2023). Although these results from a large and adequately powered trial support the efficacy of this intervention, it is not known if such findings might generalise to a population of NHS doctors, whose work demands, and resources are likely to be considerably different to those of participants in the previous trial.

In the proposed trial, this intervention will be delivered by experienced mentors who were trained and supervised by the intervention developer. To safeguard the integrity and transparency of the study, the intervention facilitators and developer are not members of the research team and will have no role in participant recruitment, data collection, data analysis or publication of the study results. All groups will be delivered online via Microsoft teams to groups of up to 30 participants per session. The intervention will consist of eight, ninety-minute interactive sessions, over ten weeks. Each workshop will be structured and delivered using a standardised presentation describing the principles of the model within that session. At specified stages of the presentation, participants will be encouraged to engage in facilitated group discussions consisting of up to 30 people. Participants will receive electronic written and didactic materials which accompany the intervention, to support the transfer of their learning into their daily work and personal life.

4.3. Measures

Primary outcome measure

Occupational burnout will be measured using the Oldenburg Burnout Inventory (OLBI), a 16-item questionnaire designed to assess two facets of burnout, emotional exhaustion (OLBI-E) and disengagement (OLBI-D), including their cognitive and somatic aspects (Demerouti, Bakker, Nachreiner, & Schaufeli, 2001). For both dimensions, four items are phrased positively and four items are phrased negatively (reverse scored). Every item is scored between 1 (strongly agree) and 4 (strongly disagree), and item ratings are averaged into a single index (range = 1 to 4), where a higher score is indicative of increased burnout. Examples of positively and negatively phrased items are: "I can tolerate the pressure of my work very well"; "During my work, I often feel emotionally drained". A psychometric validation study applying

the OLBI in 2599 adults with a variety of professional backgrounds demonstrated high internal consistency (Cronbach's alpha = .74 to .76 for each subscale) as well as robust convergent, and discriminant validity (Halbesleben & Demerouti, 2005).

Secondary measures

- Participants will also be asked to report basic demographics (age, gender, ethnicity) and generic information about their job role and work setting (speciality, qualified vs. trainee status, hours of clinical work per week).
- The Warwick-Edinburgh Mental Well-being Scale (WEMWBS) is a 14-item questionnaire; each answered on a 1 to 5 Likert scale. Items cover different aspects of eudaimonic and hedonic mental wellbeing and are worded positively. Item scores are summed to produce a total score (range: 14 to 70), where higher scores indicate greater psychological well-being. Psychometric testing has indicated that this measure was valid, reliable and acceptable measure of well-being in adult respondents (Tennant et al., 2007); with good internal consistency (Cronbach's alpha = .89 to .91) and test-retest reliability (.81). This will be collected at each of the measurement points outlined in Figure 1 (weeks 0, 10, 20, 44).
- The Job Discrepancy and Satisfaction Scale is an 8-item scale which captures how satisfied an individual is with their role, their job rewards (e.g., salary and promotion), and job resources (e.g., supervision and working conditions). Items are scored 1-4 and averaged to give the same scale score range with higher values representing greater job satisfaction. A recent study of therapist burnout reported a Cronbach α of .75 (Delgadillo et al., 2018). This will be collected at each of the measurement points outlined in Figure 1 (weeks 0, 10, 20, 44).

Other measures

- The Mental Health Professional Stress Scale is a 42-item measure which captures sources of pressure at work in mental health staff but has also been used in a wider NHS context. It contains seven, 6-item sub-scales with each item scoring 0-4, with higher scores representing a more stressful workplace. Item scores are averaged for each sub-scale and the whole scale to give scores ranging 0-4. The following 6-item sub-scales will be used (total 30-items): workload; client-related difficulties; organisational structures and processes; relationship and conflicts with other professionals; lack of resources. Cronbach's alpha values for these range between .78 and .81 (Cushway, Tyler, & Nolan, 1996). This will be collected at baseline only.
- The Overcommitment subscale of the Effort-Reward Imbalance Questionnaire (Siegrist, Li, & Montano, 2014) is a 6-item scale that captures an individual's ability to separate professional roles from personal life. The effort and reward subscales capture very similar constructs to workload and job satisfaction already provided for by separate measures and so would be superfluous. Items are scored 1-4 with one reverse scored item and averaged to give the same sub-scale score range with higher values representing greater overcommitment to work. Cronbach's alpha is reported as greater than .70 by the authors (Siegrist et al., 2014) and in a recent study of burnout values were .80 or greater and repeatable (Avanzi et al., 2014). This will be collected at baseline (week 0) and at weeks 20 and 40.

4.4. Recruitment, study procedures and data collection

Participant recruitment process

- A principal investigator (PI) will be nominated at each of the participating trial sites, and this person will be responsible for promotion and recruitment tasks described below.
- A promotion and recruitment pack will include: (1) a brief newsletter and (2) a participant information video. These promotional materials will be disseminated to the workforce by the PI via local NHS management mailing lists, via organisational communication teams, and via NHS wellbeing teams, via NHS intranet front page, and via social media campaigns, and other appropriate pathways.

- The PI will also organise attendance at relevant team meetings (e.g., meetings of clinical leaders, managers) conducted remotely (e.g., using MS Teams) to promote the study. The PI may attend one or more of these promotional meetings, but may also delegate attendance to other members of the research team.
- The promotion and recruitment period will last up to twelve weeks. Promotion activities will commence once ethical approvals have been received. The formal electronic consent process (described below) will also be activated once ethical approval is in place. Potential participants will have the opportunity to contact the research team via email to clarify questions, if necessary.
- Promotional materials described above will contain a weblink to an electronic participant information sheet and consent form (when ethical approval has been given). This method will ensure that no paper copies can be lost or misplaced in the post, and will be an efficient way to gather informed consent using an industry-standard and secure online survey system. A sample text for the consent form that will be available electronically is provided in the Appendix. NHS managers and/or team leaders will not be involved in the consenting process, which will minimise administrative burden and the potential for selection biases or the application of undue pressure on potential participants.
- Consenting participants will be randomly allocated to the online intervention groups. Allocation will be carried out by a NHS-based researcher who is independent of the core research team, using a computerized block randomization schedule. Randomisation will be communicated directly to study participants via email within one week of receipt of their electronic consent form. This email will contain further instructions on how participants can register onto an upcoming online workshop anonymously.
- The research team based at Rotherham Doncaster and South Humber (RDaSH) NHS Trust will inform the intervention facilitators when the recruitment target has been met, providing a list of consenting participants after the randomisation process has been concluded. This will ensure CPM facilitators will know how many participants to expect in each of the intervention groups, and how to address them (e.g., the list will include their first names and areas of specialty). A research assistant linked to the RDaSH research team will work closely with the CPM intervention facilitators to coordinate the organisation of the groups.

Organisation of the intervention groups

- Participants will access the intervention using video conferencing software.
- To allow flexibility and to accommodate different working patterns and shifts, participants will have the opportunity to attend one of several available groups (up to four groups will be running simultaneously) which occur throughout different days and times of the week. Participants will receive an email listing the available options, and they will select their preferred schedule.
- After participants select their preferred schedule (e.g., day/time for workshop attendance), details of the sessions, including weblinks, dates and times will be provided via email. Staff will be asked to attend the same session each week to ensure numbers are managed. However, we appreciate that shift patterns need to be accounted for so we will ask participants to notify the research team if they need to change their day on a selected week. We expect that those who agree to take part in the trial will complete eight sessions spread over ten weeks, however we understand that some will be unable to do so, therefore we will consider a participant as having dropped out of the trial if they miss four or more sessions.
- After Group 1 has completed the ten-week, eight session intervention, the second group will have access to the same intervention using the process outlined above in Figure 1.

Data collection and safeguarding procedures

All participants irrespective of group allocation will be asked to complete the primary and secondary
measures described above, at four assessment points, as described in the 'Measures' section above.
 The measures will be collected by an independent NHS-based research team, who is not involved

directly in the intervention delivery. The researchers will use a secure, web-based, data collection system called Qualtrics.

- The consent and demographic questionnaires will ask for the participant's preferred email address. This is to ensure we are able to contact the participants throughout the study period (e.g., sending email reminders). Once they have completed the consent form we will email the participants a unique participant pseudonym, which cannot personally identify any of the study participants. The participant will then use this pseudonym to identify themselves throughout the rest of the study (i.e., to log in to the Microsoft Teams webinar). The research team will keep a record of the participant's email address and associated pseudonym, so if the participant forgets their code they can contact the team to retrieve these details. Staff in the research team will schedule the MS Teams sessions and will invite participants using their email addresses (this is required for the breakout session facility to be used). All participants' email addresses will be deleted after 2 years, which is a time-scale that we expect will allow sufficient time for the study to be concluded and to enable the research team to communicate all of the relevant results to participants via email.
- The measures will be collected by the research team using a secure, web-based, industry-standard data collection system. Therefore, all data collection will be in electronic form. Participants will receive email reminders (sent confidentially by the research team) at the relevant measurement points (see Figure 1). A maximum of 3 reminder emails will be sent to non-responding participants at each of the measurement points. If participants do not respond after the 3 reminders, we will consider that specific data-point to be missing. To access the survey, each participant will click on the link to access the survey via Qualtrics.
- Pseudonymised qualitative data will be collected using the same Qualtrics survey after all participants had the opportunity to access the intervention (week 20). The purpose of collecting this information is to obtain detailed feedback about the participants' experience of being involved in the study and attending the intervention. We expect that some participants will not have been able to attend any intervention sessions, and therefore we intend to ask them for qualitative feedback to enable us to understand barriers to participation. Therefore, qualitative data will be obtained both from those who attended at least one session of the intervention and those who did not. The qualitative questions are available in the qualitative survey question document.
- The final study dataset will be archived for potential future use in secondary analyses and to contribute to systematic reviews and meta-analyses. The study documents will be stored in a secure NHS network drive, only accessible to members of the research team, which is located behind RDaSH Firewall. This will ensure the security and adequate storage of research data, consistent with NHS and academic codes of information governance and data protection.
- All analyses will be carried out at a University site, and data will be held in a restricted-access drive. The study dataset will be held at RDaSH for 10 years after the conclusion of the study.
- The University of Sheffield will be a data processor, whilst RDaSH will remain the data controller. The University of Sheffield will store anonymised data for 10 years after the conclusion of the study.

5. Data analysis

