Randomization and data collection	Consenting NHS doctors will be randomly assigned to two groups; 1 and 2. Participants in both groups will be asked to complete outcome measures at an initial baseline assessment, after which only participants in group 1 will access an 8-session, 10-week intervention (controlled phase). Next, group 2 will access the intervention during an 8-session, 10-week period (full implementation phase). Finally, we will collect further outcome measures 6 months after both groups have completed the intervention (follow-up phase). Following intention-to-treat principles, participants who do not attend any intervention sessions (and who do not formally withdraw) will be included in the study and will be invited to complete measures.	
Planned Sample Size	Minimum recruitment target of 180 participants, expecting 50% attrition, plus approx. 120 non-intervention participants.	
Data analysis method	 Trial data will be summarised using a CONSORT diagram and analyses will be based on intention-to-treat principles. The primary analysis will compare between-group differences in OLBI at 10-weeks, using ANCOVA adjusting for baseline OLBI. Secondary analyses: Between-group comparisons will be conducted at each measurement point using ANCOVA adjusting for baseline severity in the relevant outcome measure. Between-group and within-group effect sizes will be calculated using Cohen's d. Completion / dropout rates will be compared between groups using chisquare analysis. Predictors of dropout and treatment response will be examined as a secondary analysis using Elastic Net regularization Variability in burnout, wellbeing and job satisfaction will be examined across groups defined by job role and demographic characteristics using t-tests and appropriate non-parametric tests. Qualitative data will be analysed using thematic analysis. 	
Study Period	24 months (18 months active study period, plus 6 months analyses and dissemination)	

2. Background and rationale

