3.3. Hypotheses

[figure not shown]
- A) Exposure to the intervention will be associated with significantly lower mean burnout severity by comparison to a waitlist (delayed intervention) control group
- B) After the control group is exposed to the intervention, there will be no significant differences in mean burnout level between the two groups (immediate intervention group, delayed intervention group)
- C) Mean burnout severity for all participants at the end of the 6-month follow-up period will be significantly lower than baseline severity (prior to intervention), but not significantly different to endof-treatment severity, indicating maintenance of gains

4. Study design

This will be a pragmatic, stepped wedge, open-label, randomised controlled trial. Consenting doctors will be randomly assigned to two groups, by a research assistant using a computerized randomization algorithm. The randomisation sequence will be based on random blocks of 10 participants, and

stratification according to participants' employing organisation (trial site). The study will be carried out in three phases, which are illustrated in Figure 1.

Figure 1. Stepped wedge trial design

Participants in both groups will be asked to complete outcome measures during a pre-intervention baseline assessment (week 0). After the baseline assessment, only participants in group 1 will access an 8 session, 10-week intervention (controlled phase). Next, group 2 will access the intervention during a 10-week period (full implementation phase). Finally, we will collect further outcome measures 6 months after both groups have completed the intervention (follow-up phase). Selected outcome measures (see section '4.3 Measures' for more details) will be completed at each of the measurement points outlined in the above timeline (weeks 0, 10, 20, 44). All measures will be completed online using an industry-standard survey system (Qualtrics), which will be managed by a research assistant.

The end of the study is classed as once the participant has completed the six-month follow-up questionnaire. However, the participants email addresses will be kept for up to six months after this to ensure the research team can disseminate the results of the study. Following this, all personal data will be deleted.

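### The protocol lists randomisation before the week-0 baseline and nowhere requires baseline OLBI to be completed before allocation is disclosed, so the primary covariate is not protected from knowledge of allocation.

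*Protocol*

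**What the plan says.** On who is randomised, section 4.4 names consent as the only condition: "Consenting participants will be randomly allocated to the online intervention groups". On disclosure, the same section says: "Randomisation will be communicated directly to study participants via email within one week of receipt of their electronic consent form". The recruitment window is long: "The promotion and recruitment period will last up to twelve weeks".

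On order, the Synopsis row on randomisation and data collection begins "Consenting NHS doctors will be randomly assigned to two groups; 1 and 2" and continues "Participants in both groups will be asked to complete outcome measures at an initial baseline assessment". Section 4 has the same sequence, and places baseline at week 0 relative only to the start of the intervention: "Participants in both groups will be asked to complete outcome measures during a pre-intervention baseline assessment (week 0").

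On collection, section 4.4 describes the four assessment points together, week 0 included: "All participants irrespective of group allocation will be asked to complete the primary and secondary" measures. It adds "A maximum of 3 reminder emails will be sent to non-responding participants at each of the measurement points", after which the value counts as missing. The questionnaires that section 4.4 mentions alongside consent are the consent and demographic forms; OLBI is not named there.

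Section 4 calls the trial open-label. Section 4.3 makes OLBI a self-completed questionnaire. Section 5.2 adjusts the primary week-10 ANCOVA for baseline OLBI.

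**The concern.** Randomisation guarantees that a covariate is balanced in expectation only if knowledge of the allocation cannot affect it. A self-rating of burnout made by a doctor who already knows whether the course starts now or ten weeks later does not meet that condition. If the news moves the rating, it moves it differently in the two arms, and ANCOVA then adjusts for a difference that the allocation itself produced.

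Two things are at stake. First, the primary adjusted difference can be biased. The same baseline also feeds the within-group comparisons and the reliable-improvement outcome in section 5.3. Second, a doctor who loses interest on learning of a delayed start may never submit a baseline. Missing baselines could then differ by arm and would be filled in by the imputation in section 5.2.

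This is trial conduct and not something usually left to a statistical analysis plan. No analysis can recover an uncontaminated baseline afterwards.

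**Working it through.** **Step 1. The plan's own figure.** Section 5.1 gives d = 0.6, f = 0.30, alpha 0.05, power 80%, 90 analysed in total, and 180 after 50% dropout. With one covariate and two groups, the noncentral F power (denominator df N − 3, noncentrality f²N) is 0.799 at N = 89 and 0.804 at N = 90. The smallest total is therefore 90, and 90/(1 − 0.5) = 180. Both figures reproduce, and nothing in this point alters them.

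**Step 2. The order of events, side by side.**

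| Event | What fixes its timing | Tied to baseline OLBI? |
|---|---|---|
| Randomisation | Consent (4.4) | No |
| Allocation email | Within one week of consent (4.4) | No |
| Baseline OLBI | Week 0, before the intervention (4) | Not placed relative to consent or email |
| Baseline reminders | Up to three, then missing (4.4) | No cut-off at disclosure |

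Week 0 is the start of the ten-week controlled phase, and consent may be given over up to twelve weeks. If week 0 is one common date after recruitment closes (an assumption), the first doctors to consent have their allocation by week 1 of recruitment and reach week 0 at week 12. They would know their group for about 12 − 1 = 11 weeks or slightly more. Even without a common date, a cycle of three reminders can outlast the one-week limit.

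**Step 3. How a baseline shift reaches the estimate.** The adjusted difference is (Y₁ − Y₂) − b(X₁ − X₂), where Y is week-10 OLBI, X is baseline OLBI, b is the within-group slope and the subscripts are the groups. If knowing the allocation shifts X₁ − X₂ by δ and leaves week 10 untouched, the bias is −bδ. In SD units with equal variances b equals the correlation ρ, so the bias has size ρ|δ|.

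The protocol gives neither ρ nor δ; the values below are assumptions. The last two columns give the two-sided rejection rate with no true effect, from the noncentral F with noncentrality (N/4)(ρδ)²/(1 − ρ²).

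| ρ | δ (SD) | Bias (SD) | Share of 0.6 | N = 90 | N = 180 |
|---|---|---|---|---|---|
| 0.6 | 0.1 | 0.06 | 10% | 6.4% | 7.9% |
| 0.6 | 0.2 | 0.12 | 20% | 10.8% | 17.0% |
| 0.6 | 0.3 | 0.18 | 30% | 18.4% | 32.3% |
| 0.7 | 0.1 | 0.07 | 12% | 7.5% | 10.0% |
| 0.7 | 0.2 | 0.14 | 23% | 15.1% | 25.8% |
| 0.7 | 0.3 | 0.21 | 35% | 28.1% | 50.1% |

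**Step 4. Direction.** Higher OLBI means more burnout, so benefit is a negative difference. Relief in group 1 and disappointment in group 2 make X₁ − X₂ negative, so −bδ is positive and counts against the intervention. With δ of size 0.2 and N = 90, rejections in the direction of the bias rise from 2.5% to 10.5% (ρ = 0.6) or 14.9% (ρ = 0.7). Rejections in the other direction fall from 2.5% to 0.4% or 0.2%. A reaction of the opposite sign would reverse this.

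**The case against.** The strongest reply is that no sentence places baseline after the allocation email. Speaking of both groups completing a baseline is ordinary narrative, and a team could collect OLBI with consent, or in the days before the email, without breaching anything written. Some text fits that reading: demographics, which section 4.3 lists among the secondary measures, are gathered around consent, and section 4 expects to hold baseline data for doctors who never attend. The timeline in Figure 1 is also not visible in the text at hand. All of this stands. A reader might infer from the order of description that baseline is in fact collected after disclosure; the documents do not support that as a statement of fact, and the exposure of about 11 weeks rests on an assumed common start.

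The second reply concerns size. The correlation and the shift come from no passage, and at a 0.1 SD shift with 90 analysed the error rate is only 6.4% to 7.5%. The formula also supposes that the reaction has no effect at week 10. A reader might take the two-sided rates as a raised risk of falsely declaring benefit. Under the most obvious reactions they are the reverse: the extra rejections favour the wait-list. This stands too.

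What the replies do not remove is the gap itself. Disclosure is tied to consent, baseline is tied to week 0, and nothing links the two.

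**Conclusion.** The concern holds in this form: the protocol describes randomisation before baseline, emails the allocation within a week of consent, and has no rule that baseline OLBI must be in hand first. Followed as written over a recruitment period of up to twelve weeks, it allows the covariate of the primary analysis to be rated with knowledge of allocation, and allows baseline non-response to differ by arm.

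The size cannot be derived from the protocol. The illustrative bias of 0.06 to 0.21 SD (10% to 35% of the planned effect) depends wholly on the assumed correlation and shift, and its direction is unknown. The case for change rests on the missing safeguard and its low cost, not on a demonstrated bias.

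**What to change.** State one order in the Synopsis, section 4 and section 4.4: consent, baseline measures submitted and locked, randomisation, allocation email. Make a submitted baseline a condition of randomisation, or at least of releasing the allocation email, and let the one-week limit for that email run from baseline submission. Say how doctors who consent but never submit a baseline will be shown in the CONSORT diagram. Randomising everyone in one batch when recruitment closes is optional; the gate alone removes the problem.

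If any allocation has already been released, record for each participant whether the baseline time stamp precedes the email, report this by arm, and add an unadjusted week-10 comparison as a sensitivity analysis. That comparison does not carry a baseline shift through the covariate adjustment, though it is less precise.

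The cost is a protocol amendment and a reordering of the survey. Some baselines would be taken several weeks before the intervention: at most 12 weeks before week 0 if week 0 is a common date after recruitment, and so up to 12 + 10 = 22 weeks before the primary outcome. This may slightly weaken the covariate correlation. The sample size stays at 90 analysed and 180 recruited; section 5.1 converts d to f as 0.6/2 = 0.30, with no explicit credit for that correlation.
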